1. SYNOPSIS

Study Title	SeveriTy of Pulmonary Edema and timing of Resolution in patients with severe pre-eclampsia and eclampsia (TIPER) – a prospective observational study		
Internal ref. no. (short title)	Pulmonary edema resolution in severe pre-eclampsia and eclampsia – TIPER		
Study Design	A prospective, observational cohort st	udy.	
Study Participants	Female subjects, hospitalized with seven	ere preeclampsia or eclampsia	
Planned Sample Size	All eligible patients admitted to PCMH for 1 year		
Study Site	Princess Christian Maternity Hospital,	Freetown, Sierra Leone	
Planned Study Period	April 2023 to April 2024.		
Inclusion criteria	All patients with severe pre-eclampsia during the study period	or eclampsia admitted to hospital PCMH	
Exclusion criteria	 Patients with chronic hypertensive disorders Lung ultrasound not feasible, e.g., due to electricity breakdown, or absence of the trained sonographer or presence of subcutaneous emphysema, 		
Aim	The primary aim is to describe the frequency of lung ultrasound consistent with pulmonary oedema and the timing of resolution after delivery. Secondary aims include the assessment of the frequency of acute respiratory		
	failure, other LUS findings beyond pulmonary edema, the assessment of oxygenation, the use of respiratory organ support strategies, assessment of cardiac function, and quantification of major direct/ indirect obstetric complications and of perinatal complications.		
Hypothesis	 A high proportion (>20%) of patients show LUS signs consistent with pulmonary edema before delivery. There is incomplete resolution of both clinical and ultrasound signs of pulmonary edema 48 hours after delivery. 		
	Objectives	Outcome Measures	
Primary	Frequency of LUS consistent with pulmonary edema	Frequency endpoint: proportion of patients with a LUS positive for pulmonary edema Severity: LUS areation score	
	Timing of resolution after delivery	Categorical: Fraction of patients with improvement or resolution of LUS findings. Numerical: delta LUS score between T1 and T2	
Secondary	Frequency of acute respiratory failure in patients with Severe Pre eclampsia and in patients with Eclampsia	Proportion of patients with acute respiratory failure	

	Frequency of other LUS findings	 Proportion of patients with consolidations isolated pleural effusion 	
		minor LUS findings	
	Frequency of organ support strategies	Fraction of patients that receive oxygen and/or CPAP and/or mechanical ventilation	
	Frequency of patients with abnormal cardiac function	Defined as low cardiac index measured by ultrasound	
	Oxygenation assessment	SpO_2 to FiO_2 ratio	
	Frequency of Major Direct Obstetric Complications (MDOCs)	Fraction of patients with at least one additional MDOC (antepartum hemorrhage, postpartum hemorrhage, sepsis, uterine rupture, obstructed labour)	
	Frequency of Indirect Obstetric complications	Fraction of patients with at least one among stroke, severe malaria, acute kidney injury and cardiac insufficiency.	
	Frequency of perinatal complications	Intra uterine fetal death (IUFD), Apgar score, Admission to special care baby unit (SCBU)	
Procedures	All procedures are standard of care and routinely performed in critically ill patients:		
	 Lung Ultrasound examination Echocardiography and inferior vena cava ultrasound Pulse oximetry Urine output monitoring (when foley catheter inserted by treating team) 		
Safety	The bedside non-invasive procedures pose minimal risk to the patient and do not require additional transportation.		
Benefits of study	The study will evaluate the possibility of early intercepting pre-eclamptic and eclamptic patients with pulmonary involvement. This group of patients may potentially benefit from the implementation of optimal triage and early therapeutic choices in a limited resource setting (e.g. diuretics, escalation to non-invasive or invasive ventilation, referral to HDU or ICU, dialysis) with a potential to reduce unfavourable outcomes.		

2. ABBREVIATIONS

ARDS	Acute respiratory distress syndrome	
РСМН	Princess Christian Maternity Hospital	
CUAMM	Doctors with Africa – CUAMM	
HDU	High Dependency Unit	
FiO ₂	Fraction of inspired oxygen	

LUS	Lung ultrasound
SLERC	Sierra Leonel research ethics committee
SpO2	Peripheral oxygen saturation

3. BACKGROUND AND RATIONALE

3.1 Background

Obstetric critical care burden in resource-poor settings

Maternal mortality from treatable causes concerning the critical care domain in low– income countries remains strikingly high (1). Maternal mortality in Sierra Leone is the highest in the world with 1,360 deaths per 100,000 born alive. The burden of obstetric–related critical care morbidity is also extremely high. In high–income countries less than 2% of intensive care unit (ICU) admissions relate to obstetric illnesses, but these rise to 10% in resource–limited settings. Pre-eclampsia/eclampsia are hypertensive disorders of pregnancy, one of the 3 leading causes of maternal morbidity and mortality worldwide(2).

Aims of critical care management

The aims of critical care management are to stabilize and monitor physiological parameters and support failing organ systems, thus allowing time for recovery and implementation of disease—specific therapies. Supportive management is classically divided by organ systems and may be guided by invasive or non–invasive monitoring, globally aimed at adequate oxygen delivery to the tissues. This involves several steps, at any of which deficiencies may occur, i.e., oxygen transfer to the blood in the lungs, oxygen transport from the lungs to the tissues and finally diffusion from capillary blood to the cells (3). The respiratory system is a central in this process; hence early and precise assessment of pulmonary impairment is pivotal.

Pulmonary complications associated with Severe Preeclampsia and Eclampsia

The reported incidence of eclampsia is 1.6 to 10 per 10,000 deliveries in developed countries, whereas it is 50 to 151 per 10,000 deliveries in developing countries (4–6). In addition, low-resource countries have substantially higher rates of maternal and perinatal mortalities and morbidities. This disparity in incidence and pregnancy outcomes may be related to universal access to prenatal care, early detection of preeclampsia, timely delivery, and availability of healthcare resources in developed countries compared to developing countries. Because of its infrequency in developed countries, many obstetrical providers and maternity units have minimal to no experience in the acute management of eclampsia and its complications.

Respiratory distress and pulmonary oedema are known complications of preeclampsia-eclampsia and their insurgence is a hallmark of severe disease (7,8). Pulmonary oedema is reported as a complication in 2.9% of patients with preeclampsia-eclampsia (9). Pulmonary involvement is associated with worse maternal and perinatal outcomes (10,11). Incidence is significantly higher in low income countries, rising to 12% due to poorer prenatal care and access to hospital care, and suboptimal diagnostic and management processes (12).

A retrospective study showed how the average time to resolution of pulmonary oedema for obstetric patients with different primary clinical disorders was 2.4 days (13). The preeclamptic and eclamptic patients is characterized by systemic endothelial cell dysfunction, increased systemic vascular resistance and increased capillary permeability, all leading to excessive extravasation and as such increasing the risk of pulmonary oedema (14,15). This is also why, together with the infectious cause, preeclampsia/eclampsia are the leading cause of ARDS in pregnancy (16,17).

Challenges with diagnosis and follow up of pulmonary complications

In the absence of imaging modalities (chest radiography, computed tomography) and laboratory measures (blood gas analysis) it may be difficult to quantify respiratory deterioration, or the pulmonary component in a global deterioration. Bedside clinical examination lacks sufficient sensitivity and specificity for

pulmonary edema and ARDS. Simple bedside techniques are increasingly available, such as pulse oximetry for quantification of oxygenation deficit and lung ultrasound for systemic imaging.

Use of lung ultrasound to detect pulmonary complications

Point–of–care lung ultrasound (LUS) is a non–invasive, rapid and sensitive method to detect pulmonary pathology (18,19). LUS is a bedside practical and easy tool to use, and being a radiation–free investigation it can be regularly repeated. LUS may expedite etiological diagnosis in cases of undifferentiated dyspnoea (20), both in resource–rich and –poor settings (21,22). Detection of focal consolidation could suggest a diagnosis of pneumonia, whereas the visualization of multiple complex patterns could suggest ARDS (23). Simultaneous presence of pleural fluid and loss of aeration may point at fluid overload (24). Conversely, a normal lung pattern in the presence of respiratory distress would direct the clinician towards alternative diagnoses, such as respiratory compensation of a metabolic acidosis, asthma or pulmonary embolism (25).

Additional point-of-care ultrasound applications

Point-of-care *echocardiography* also represents a potential valuable adjunct to clinical care in low- and middle-income countries, with several ultrasound-based clinical algorithms proposed. Early bedside echocardiographic assessment of cardiac function is recommended to guide haemodynamic management and when combined with lung ultrasound it provides further clinically relevant information. The basic echocardiography examination consists of five standard views and allows the physician to: (i) identify imminent life-threatening causes of haemodynamic failure, (ii) recognise coexisting diagnoses that complicate management, (iii) follow the evolution of the disease process, and (iv) monitor response to treatment.

3.2 Rationale

Accurate assessment of patients with pulmonary involvement combined with LUS and echocardiography could lead to earlier detection of pre eclampsia and eclampsia associated pulmonary oedema, ARDS and other pulmonary complications. As there is currently limited evidence regarding the features, severity, aetiology and history of pulmonary oedema in this kind of people (26,27), the data from this prospective, cohort study might facilitate the early intercepting pre-eclamptic and eclamptic patients with pulmonary involvement to implement optimal triage and early therapeutic choices in a limited resource setting (diuretics, escalation to non invasive or invasive ventilation, referral to HDU or ICU, dialysis) could reduce unfavourable outcomes.

4. OBJECTIVES AND OUTCOME MEASURES

Objectives	Outcome Measures	
Primary objective		
To describe the frequency of LUS abnormalities consistent with pulmonary oedema	Frequency endpoint: proportion of patients with LUS consistent with pulmonary edema Severity endpoint: LUS aeration score (numerical 0 to 36)	
To describe the timing and entity of edema resolution after delivery	Frequency endpoint: Fraction of patients with improvement or resolution of LUS findings. Quantitative endpoint: delta LUS score between T1 and T2	
Secondary objectives: To describe the frequency of acute respiratory failure in patients with Severe Pre- eclampsia and in patients with Eclampsia	Proportion of patients with acute respiratory failure (see definition)	
Frequency of other LUS findings	 Proportion of patients with: consolidations isolated pleural effusion minor LUS findings Calculation of the LUS ARDS score 	
Frequency of organ support strategies	Fraction of patients that receive: - oxygen - CPAP - Mechanical ventilation	
Frequency of patients with abnormal cardiac function	Defined as either low cardiac output measured by ultrasound	
Oxygenation assessment	SpO ₂ to FiO ₂ ratio	
Frequency of Major Direct Obstetric Complications	Fraction of patients with at least one additional MDOC (APH, PPH, sepsis, uterine rupture, obstructed labour)	
Frequency of Indirect Obstetric complications	Fraction of patients with at least one among stroke, severe malaria, acute kidney injury and cardiac insufficiency	
Frequency of perinatal complications	IUFD, Apgar score, Admission to special care baby unit (SCBU)	

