4.1 Hypothesis

- 1. A high proportion (>20%) of patients show LUS signs consistent with pulmonary edema before delivery.
- 2. There is a resolution of both clinical and ultrasound signs after in the 48 hours after delivery.

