6.4. Case definitions

Acute respiratory failure defined as RR≥30 breaths per minute AND/OR SpO₂/fraction of inspired oxygen (FiO₂) \leq 315 AND/OR signs of difficult breathing, including the use of accessory muscles or nasal flaring. FiO₂ will be derived from the amount of oxygen the patient receives in liters.

Clinical pulmonary oedema

Defined as respiratory distress (respiratory rate >30 breaths/min and/or SpO2 <92% on room air) with bilateral fine crepitations on chest auscultation.

Lung ultrasound consistent with pulmonary oedema (categorical)

The presence of three or more B-lines (any size and any distance apart) in a particular lung region will define a positive lung region for interstitial syndrome (30) Pulmonary edema will be defined as the presence of \geq 2 positive regions per side.

Abnormal lung ultrasound aeration score

The LUS aeration score (numerical) will be calculated: each lung field will be scored from 0 to 3 as follows: "0," A-pattern with \leq 2 B-lines; "1," more than 2 separated B-lines; "2," multiple coalescent B-lines; or "3," lung consolidation, defined as anechoic or tissue-like images arising from the pleural line that is limited in depth by an irregular border. A global LUS score will be calculated at each time point and ranged from 0 to 36.

LUS ARDS score

The three variables included in the final logistic regression model for diagnosis of ARDS are: left LUS aeration score (range 0-18), right LUS aeration score (range 0-18), and the number of antero-lateral lung regions with an abnormal pleural line (range 0-8). The LUS-ARDS score can range from 0 to 91 and is computed with the formula below. (31)

LUS-ARDS score = 2.5 x left LUS aeration score + 1 x right LUS aeration score + 3.5 x no. of anterolateral regions with an abnormal pleural line

Acute Respiratory Distress Syndrome (ARDS)

Defined according to the Berlin Definition or Kigali Modification as shown in **Table 1**.

Criteria	Berlin definition of ARDS	Kigali modification
Timing	Within 1 week of a known clinical insult, or new or worsening respiratory symptoms	
Oxygenation	PaO ₂ /FIO ₂ ≤300 mmHg SpO ₂ /FIO ₂ ≤315 mmHg	
PEEP requirement	Minimum 5 cm H ₂ O PEEP required by invasive mechanical ventilation (non-invasive acceptable for mild ARDS)	No PEEP requirement, consistent with AECC definition

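### The categorical primary resolution endpoint pools improvement with resolution and is not restricted to patients with LUS oedema at T1, so its value cannot show how often oedema resolves

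*Combined protocol and SAP*

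**What the plan says.** Section 4 (Objectives and Outcome Measures) lists, under the primary objective on timing and extent of resolution, a frequency endpoint, "Fraction of patients with improvement or resolution of LUS findings", and a companion measure, "Quantitative endpoint: delta LUS score between T1 and T2". The Synopsis repeats the pooled wording: "Categorical: Fraction of patients with improvement or resolution of LUS findings".

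Hypothesis 2 concerns resolution, but its two wordings point in opposite directions. Section 4.1 has "There is a resolution of both clinical and ultrasound signs after in the 48 hours after delivery"; the Synopsis has "There is incomplete resolution of both clinical and ultrasound signs of pulmonary edema 48 hours after delivery".

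Section 6.4 gives the building blocks. A region is positive on "The presence of three or more B-lines (any size and any distance apart) in a particular lung region"; LUS oedema requires at least two positive regions on each side; the global score runs from 0 to 36. No section defines improvement or resolution, or says who is in the denominator.

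Section 5 places the second assessment 24 to 72 h after delivery and allows a post-delivery scan alone when the first is not feasible. Section 10 names non-resolution of interstitial syndrome at 48-72 h as one outcome for regression. It plans an inter-observer kappa on 10 cases and gives no sign that this will set a threshold for change.

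**The concern.** A patient who resolves will normally also have a lower score, so improvement absorbs resolution and the pooled fraction cannot be taken apart afterwards. A high value fits both a cohort in which oedema clears and one in which it lessens but persists. Those are the two states that the two wordings of hypothesis 2 set against each other.

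Two open choices add to this. If T1-negative patients are counted, they dilute resolution, because they have no oedema to resolve. If any fall in score counts, reading error alone produces improvement. With neither choice fixed in advance, threshold and denominator could be settled after the data are seen, for a primary endpoint.

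**Working it through.** The plan gives no expected resolution rate, event count or sample size, so there is no figure of its own to reproduce. T1 is taken as the pre-delivery scan and T2 as the scan at 24 to 72 h.

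**1. Pooling (no assumption about error).** Take a patient with all 12 regions scored 1: score 12 × 1 = 12. At T2, three regions per side still score 1 and the rest 0: score 6 × 1 = 6. Three positive regions per side still meets the Section 6.4 rule of at least two. If every oedema patient follows this course, the pooled fraction among them is 100% and the proportion resolved is 0%.

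**2. Denominator.** If π is T1 prevalence and r the proportion of cases that resolve, the all-patient resolution fraction is π × r, with maximum π. Hypothesis 1 reads "A high proportion (>20%) of patients show LUS signs consistent with pulmonary edema before delivery". At that threshold the maximum is 0.20 × 1 = 20%, even if every case clears.

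**3. Reading error (assumed rates; the documents give none).** Each of 12 regions is misread by one grade with probability q, independently between regions and scans, with no true change. Simulated probability that the score falls by 1 point or more:

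| q per region per scan | Regions scored 0/1/2/3 in 40/35/20/5%, errors cut off at 0 and 3 | Regions 70/25/5/0%, errors cut off at 0 and 3 | True score 0, 4, 12 or 18, errors at 0 and 3 turned inward |
|---|---|---|---|
| 5% | 26% | 24% | 29% |
| 10% | 34% | 32% | 36% |
| 20% | 39% | 38% | 40-41% |

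The first mix is far sicker than hypothesis 1 envisages. With 60% of regions positive, P(at least 2 of 6) = 1 − 0.4^6 − 6 × 0.6 × 0.4^5 = 0.959, and 0.959² = 92% of patients are oedema-positive. The second is closer: 1 − 0.7^6 − 6 × 0.3 × 0.7^5 = 0.580, and 0.580² = 34%. The result changes little between them.

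**4. Denominator and error together.** Suppose all patients are counted, any fall is improvement, π = 20%, and an unchanged patient shows a fall with probability 0.292 (q = 5%, inward errors). If every resolver shows a fall, the pooled fraction is 0.292 × (1 − 0.2r) + 0.2r:
- r = 0: 29.2%
- r = 0.5: 0.292 × 0.9 + 0.1 = 36.3%
- r = 1: 0.292 × 0.8 + 0.2 = 43.4%

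The whole range of true resolution, 0% to 100%, moves the endpoint by about 14 percentage points.

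**5. Noise in the alternative.** Restricting to T1-positive patients selects on a noisy classification. With the 70/25/5/0% mix and no true change, about 14%, 23% and 32% of T1-positive patients no longer meet the rule at T2 at q = 5%, 10% and 20%. Their mean delta LUS is about −0.16 at q = 5% and −0.50 at q = 20%; in all patients it is about 0.

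**The case against.** The strongest reply is that the plan does not adopt the rules in steps 2 to 4. It does not say that any improvement counts, nor that all patients form the denominator. The row concerns oedema resolution, so patients with findings at T1 are a natural reading, and the denominator cannot literally be everyone because some women have only a post-delivery scan. This stands: threshold and denominator are undefined, not fixed wrongly. Step 1 is untouched, since it applies even with the favourable denominator.

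A reader might infer that the study cannot answer hypothesis 2 at all. The documents do not support that. Paired scans and a patient-level oedema rule exist, and Section 10 names a non-resolution outcome. But that outcome appears only as a regression outcome, at 48-72 h, which leaves out scans at 24 to 48 h, and Section 6.4 defines interstitial syndrome by region. It does not replace the primary endpoint.

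A reader might also infer that new oedema after delivery goes unseen. It does not: it raises the score and enters delta LUS. It is only not reported separately.

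Improvement is a fair part of the extent of resolution, and the study is descriptive with no success criterion. Both argue for reporting improvement, not for merging it. Finally, the error rates are assumed, and a sonographer's consistent bias would cancel between scans.

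**Conclusion.** The concern holds for this endpoint. That the pooled fraction does not identify the resolution proportion follows from the text alone: 100% on the endpoint is compatible with 0% resolved. The 20% ceiling applies only if T1-negative patients are counted. The noise figure, about a quarter to two-fifths of unchanged patients, applies only if a 1-point fall counts, and rests on assumed independent one-grade misreading of 5% to 20% of regions.

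Two further steps may tempt a reader and are not supported. One is a 3-point cut-off for improvement: nothing in the documents justifies it, and a two-reader kappa on 10 cases is too small, and not repeat-scan error, to set a stable threshold. The other is making delta LUS primary in T1-positive patients, which would bring in the regression to the mean shown in step 5.

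The sponsor should make the change: it affects a primary endpoint and costs little.

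**What to change.** In Section 4 and the Synopsis, split the categorical endpoint:

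1. Resolution: among patients with both scans who meet the Section 6.4 LUS oedema rule at T1, the proportion no longer meeting it at T2, with a 95% confidence interval.
2. Improvement without resolution: a separate category, with a minimum change fixed and justified before analysis.
3. T1-negative patients: reported separately, including new oedema at T2.

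Keep delta LUS in all patients with both scans, and show it by T1 status as descriptive only.

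Reconcile the two wordings of hypothesis 2 (Synopsis and Section 4.1) and the time windows: 48 h in the hypothesis, 24-72 h in Section 5, 48-72 h in Section 10. Hypothesis 2 also covers clinical signs, which neither resolution endpoint includes; state how they will be handled.

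Cost: rewording, with no new scans or data. The interval widens. At 50% resolution the approximate 95% half-width is 1.96 × √(0.25/n) = 0.98/√n. The plan gives no sample size; if 100 to 300 patients had both scans (an assumption) and 20% were T1-positive, n would be 20 to 60 and the half-width ±22 to ±13 percentage points, against ±10 to ±6 with everyone counted. Some apparent resolution will be regression to the mean from selecting on T1 status; state this as a limitation.

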4.1 Hypothesis

- 1. A high proportion (>20%) of patients show LUS signs consistent with pulmonary edema before delivery.
- 2. There is a resolution of both clinical and ultrasound signs after in the 48 hours after delivery.

5. STUDY DESIGN

This will be a single centre, prospective, cohort study of patients with severe pre-eclampsia and eclampsia. The expected duration of study is 1 year. All patients with suspected severe pre-eclampsia or eclampsia will undergo screening upon admission to HDU and the Eclamptic ward. Eligible patients will undergo a systematic clinical and LUS examination, straight after admission (**before delivery**). Clinical examination will focus on signs of respiratory, neurologic and cardiac failure. Lung ultrasound will be performed using a MyLab[™]Five ultrasound machine (Esaote Spa, Genova, Italy) and a low frequency (2.5–5 MHz) convex probe or a Butterfly ultrasound probe (Butterfly, USA). Lung ultrasound will be performed using the

validated 12-region method, evaluating 2 anterior regions, 2 lateral regions and 2 posterior in each hemithorax (18,28,29). As heart failure is a common finding in preeclamptic women, echocardiography performed with a cardiac sector probe, will enable real-time assessment of maternal cardiac contractility and cardiac output. The same clinical, LUS and echocardiographic assessment will be repeated between 24 h to 72 h (after delivery). Whenever the pre-delivery timepoint is not feasible due to late arrival, emergency scenario or postpartum onset, the after delivery examination only will be performed.

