10. STATISTICS AND ANALYSIS

For descriptive purposes continuous and ordinal variables data will be expressed as median with interquartile range. For categorical variables, percentages are calculated. Student's t-test or analysis of

variance (ANOVA) will be used to compare normally distributed numerical variables. Mann Whitney Utests and Kruskal-Wallis tests will be used to compare numerical variables when normality cannot be assumed, while chi-squared tests will be used to compare categorical variables. Univariate logistic regression analyses will be performed to identify potential factors associated with the clinical outcomes including, but not limited to, presence of interstitial syndrome, non-resolution of interstitial syndrome at 48-72h, development of ARDS and death in hospital. Multivariable logistic regression models will be used to identify independent risk factors for the same clinical outcomes. A forward and backwards stepwise approach will used to include variables into the models, with a limit of P <0.2.

Inter– observer variability of the lung ultrasound score between the study sonographer and an independent expert will be calculated on a random sample of 10 cases (120 lung regions) using Cohen K-statistics. Statistical analyses will be conducted using R (www.r-project.org). A P-value of <0.05 will be considered statistically significant. Analyses will be conducted after the end of patient recruitment and no interim analyses are planned. Statistical analysis will be performed with R software (R Foundation for Statistical Computing, Vienna, Austria).

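### The T1-to-T2 change starts at an admission scan with no limit on the time to delivery, so the endpoints for resolution after delivery combine change before and after delivery

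*Combined protocol and SAP*

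**What the plan says.** Section 5 (Study Design) gives the only two-scan scheme in the document. The first examination is tied to admission and takes place before delivery: "Eligible patients will undergo a systematic clinical and LUS examination, straight after admission". The second is tied to delivery: "The same clinical, LUS and echocardiographic assessment will be repeated between 24 h to 72 h (after delivery". The one exception is for women without a pre-delivery scan: "Whenever the pre-delivery timepoint is not feasible due to late arrival, emergency scenario or postpartum onset, the after delivery examination only will be performed".

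Section 4 lists as a primary objective "To describe the timing and entity of edema resolution after delivery". It has two endpoints: "Fraction of patients with improvement or resolution of LUS findings" and "Quantitative endpoint: delta LUS score between T1 and T2". The synopsis carries the same pair. Hypothesis 2 in section 4.1 is also counted from delivery: "There is a resolution of both clinical and ultrasound signs after in the 48 hours after delivery". The synopsis words that hypothesis as incomplete resolution, but counts from the same origin.

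Section 10 includes "non-resolution of interstitial syndrome at 48-72h" among the logistic regression outcomes. It names no restriction, stratum or covariate for the time from first scan to delivery.

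T1 and T2 are never defined. Reading T1 as the admission scan and T2 as the post-delivery scan is an inference from section 5, but no other scheme is offered. The reference scan for the improved or resolved fraction is not stated either, and T1 is the natural one.

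**The concern.** The two scans have different clocks. A woman who delivers a few hours after her admission scan and a woman who delivers several days after it both enter the analysis with a change described as following delivery. In the first woman the description is nearly right. In the second, much of the observed change may be antepartum.

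This can mislead in both directions. Oedema seen at admission that clears before delivery is counted as post-delivery resolution. Oedema that appears between the first scan and delivery makes the woman negative or mild at T1. If it is still there at T2 she seems to worsen after delivery, and if it has gone her postpartum clearing is missed. Two scans alone cannot separate the components.

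What is at stake is the second primary objective. The regression for non-resolution is exposed too: a factor related to how soon a woman delivers could appear related to non-resolution only because it shortens or lengthens the observation window. The frequency objective is less affected, although an admission scan can miss oedema that arises later but before delivery.

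**Working it through.** The plan states no sample size, event count or power for this objective, so there is no figure to reproduce. What follows shows how the size depends on an interval that the documents do not give.

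**Inputs**
- T2 at t = 24, 48 or 72 h after delivery (section 5 window and its midpoint).
- Mean resolution time m = 2.4 days = 57.6 h (section 3.1, from a retrospective study of mixed obstetric disorders).
- Interval from T1 to delivery, L: assumed at 6 h, 24 h, 72 h and 168 h.
- Share p of T1-positive women with the long interval: assumed 25%, varied below.
- Assumed model: exponential clearing from T1, unaffected by delivery, with no new onset.

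**Step 1. Share of the T1-T2 window that lies before delivery, L/(L + t)**

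| L | T2 at 72 h | T2 at 24 h |
|---|---|---|
| 6 h | 6/78 = 8% | 6/30 = 20% |
| 24 h | 24/96 = 25% | 24/48 = 50% |
| 72 h | 72/144 = 50% | 72/96 = 75% |
| 168 h | 168/240 = 70% | 168/192 = 88% |

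**Step 2. Share of T1 oedema already clear at delivery, 1 − exp(−L/57.6)**

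10% at 6 h, 34% at 24 h, 71% at 72 h, 95% at 168 h.

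**Step 3. Net inflation of the resolved fraction**

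The observed fraction for a woman with interval L is 1 − exp(−(L + t)/57.6). Had T1 been at delivery it would be 1 − exp(−t/57.6). The inflation in the whole T1-positive group is p times the difference, taking the other women as scanned at delivery. For L = 72 h and p = 0.25:

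| T2 | Observed, L = 72 h | T1 at delivery | Difference × 0.25 |
|---|---|---|---|
| 24 h | 0.811 | 0.341 | 0.470 × 0.25 = 11.8 points |
| 48 h | 0.8755 | 0.5654 | 0.3101 × 0.25 = 7.8 points |
| 72 h | 0.918 | 0.713 | 0.204 × 0.25 = 5.1 points |

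**Step 4. Range over the assumed inputs, T2 at 48 h**
- p = 25%, L varied: 0.043 × 0.25 = 1.1 points (6 h); 0.148 × 0.25 = 3.7 points (24 h); 7.8 points (72 h); 0.411 × 0.25 = 10.3 points (168 h).
- L = 72 h, p varied: 0.310 × 0.10 = 3.1 points; 7.8 points at 25%; 0.310 × 0.50 = 15.5 points.
- If every woman had L = 24 h, the resolved fraction would read 71% instead of 57%.

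The model excludes new onset by construction, so it can only show upward bias. Onset between T1 and delivery would pull the other way.

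**The case against.** The strongest reply is that nobody knows whether the gap is long. The documents give no admission-to-delivery interval, and section 5 itself mentions late arrival and emergencies, so some women will have little or no pre-delivery time. The 2.4-day mean comes from mixed disorders and is not an LUS measure in pre-eclampsia, and the exponential form is assumed. All of this stands, and it is why the figures above are illustration only.

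A second reply is that the study is descriptive and makes no claim about an effect of delivery. A woman clear before delivery and still clear at 48 h is correctly classed as resolved by 48 h. This stands for status at a postpartum time. It does not rescue the delta or the improved fraction, which measure change, nor an objective that asks about the timing of change after delivery.

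Three stronger readings are tempting, and the documents support none of them.
- A reader might take 0.25 × 0.71 = 18 points as the inflation. That counts everyone clear by delivery, including women who would have cleared by T2 anyway. The net figure under the same model is 5 to 12 points.
- A reader might infer that the endpoints overstate resolution. Worsening before delivery has the opposite effect, so the net direction is unknown.
- A reader might infer that the times are not collected. The case report form is not among the documents, and a T2 window counted from delivery already requires the delivery and T2 times.

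A reader might also want to exclude every woman scanned more than, say, 24 h before delivery. The documents give no basis for that cut-off. Under the model above it still allows up to 34% of T1 oedema to clear before delivery. It also narrows a cohort meant to take all eligible patients, and if delivery timing is related to severity (an assumption) it adds selection.

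**Conclusion.** The point holds as a mismatch between measurement and label. T1 is set by admission and T2 by delivery. The interval between T1 and delivery is neither limited nor analysed, and the resulting change is assigned to the period after delivery. This rests on reading T1 as the admission scan, which section 5 supports.

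The size and direction of the bias cannot be established from the documents. It is small if delivery follows admission within hours and may dominate if it follows after days. Without reporting the interval, the study could not show which case applies. The matter should be corrected because the remedy is cheap and determines what the second primary objective can conclude. It does not invalidate the study.

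**What to change.** - Define T1 as the admission scan and T2 as the post-delivery scan, and state that improvement and resolution are judged against T1.
- Record the date and time of T1, delivery and T2.
- Keep all women with paired scans. Label the overall delta and the improved or resolved fraction as change from admission to after delivery.
- Report the distribution of the T1-to-delivery interval. Present both endpoints by interval strata whose boundaries are set and justified before the outcome data are examined. Base any statement about resolution after delivery on the short-interval stratum, and acknowledge that some antepartum change remains even there.
- Include the interval as a covariate in the regression for non-resolution in section 10, preferably kept in the model whatever the stepwise procedure selects.

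Cost: wording, up to three time fields and a few extra tables, with no new scans and no change to care. The short-interval stratum will be smaller, less precise and possibly a selected group, which should be reported as a limitation. If data collection has already begun, any missing times would have to be sought in the medical chart, which section 11.2 names as the data source.
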